10.3 Causality assessment

The Site PI will determine the relationship of adverse events to the research intervention using the following scale:

- Definite = AE is clearly related to the study procedures
- Probable = AE is likely related to the study procedures
- Possible = AE is possibly related to the study procedures
- Unlikely = AE is doubtfully related to the study procedures
- Unrelated = AE is clearly not related to the study procedures

Additionally, AEs will be considered “probably related” to study procedures if one of the following happens:

- Fall; OR
- Local anesthetic toxicity or allergy

10.1. Procedures for recording and reporting adverse events

All serious adverse events that occur from the time the subject provides informed consent through and including 28 calendar days after the procedure will be recorded. Non-serious adverse events that occur from the time the study procedures begin to the end of the last study visit will be recorded.

10.4 Other reportable events

Reporting timeframes begin when the site learns of the occurrence of the event.

Event	Definition	Reporting
Breach of confidentiality	The exposure of any study information or communications directly related to a study subject to anyone not named as study staff or the release of a study subject's identifiable information to study staff who were not specified to receive such information in the protocol or IRB application.	Treat as major deviation (below)
Protocol deviation	A deviation is an incident involving a departure from the IRB-approved protocol in the actual conduct of the study. Deviations may result from the action of the participant, investigator, or staff.	See below

Event	Definition	Reporting
Major deviations	Deviations are considered major when the unapproved change(s) in previously approved research activities, implemented without IRB approval, may potentially adversely affect subjects' rights, safety, welfare, or willingness to continue participation, or affect the scientific design of the study and/or the integrity of the resultant data.	Treat as an Unanticipated Problem (above)
Minor deviations	Deviations are considered minor when the unapproved change(s) in previously approved research activities, implemented without IRB approval, do not adversely affect subjects or the integrity of the study data.	Sites are to report cumulative events to AE Coordinator at time of continuing review.
Protocol violation	An incident involving an intentional deviation from the IRB-approved protocol that was not implemented in response to an emergency situation and that may impact a subject's rights, safety, and/or welfare, makes a substantial alteration to risks to subjects, or affects the scientific design of the study and/or the integrity of the resultant data. Violations may also be repeated deviations (major or minor) of the same nature. Violations can represent serious or continuing non-compliance with the federal regulations and guidelines for ethical conduct of human subject research.	Treat as an Unanticipated Problem (above)
Protocol Exceptions	A protocol exception is an IRB-approved deviation for a single subject or a small group of subjects, but is not a permanent revision to the research protocol.	Protocol exceptions must be approved by local IRB prior to implementation.

11. Trial safety monitoring

11.1 Data Safety Monitoring Committee

After 15 subjects have been recruited, the study data will be reviewed by an independent anesthesiologist, blinded to study arm assignment, to ensure that no safety concerns exist. In the unlikely event that there is a safety concern, study recruitment will be halted and an independent Data Safety Monitoring Committee (DSMC), consisting of a minimum of three qualified practitioners, will be convened to evaluate the safety concern and make recommendations regarding changes to the study methods or termination of the study.

12. Administrative requirements

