10.5 Other reportable events.....	18
11. Trial safety monitoring.....	19
11.2 Data Safety Monitoring Committee	19
12. Administrative requirements.....	20
12.1 Good clinical practice	20
12.2 Data quality assurance	20
12.4 Study monitoring.....	20
12.5 Ethical consideration	20
12.6 Patient confidentiality	20
12.7 Investigator compliance	20
12.8 Subject cost and payment	21
13. Funding sources.....	21
References	21

Schedule of activities

	Screening Visit 1	Procedure Visit 2	Post-Adductor Block Visit 3	PACU Visit 4	24-hours Post-op Visit 5	48-hours Post-op Visit 6
Window	Up to 60 days before surgery	Morning of Surgery	15 minutes after adductor block placed +/- 10 mins	Following surgical procedure	24 hours post-op +/- 6 hours	48 hours post-op +/- 6 hours
Screening and Eligibility	X	X				
Informed Consent	X	X				
Demographics	X	X				
Medical History	X	X				
Quadricep motor strength and adductor strength assessment (Kiio sensor)		X	X			
Sensory Leg Exam ¹		X	X			
Questionnaires and Scores ²	SOC	SOC				
Pain Questionnaire ³				X	X	X
Physical Therapy Assessment and Walk Test ⁴					X	X
Concomitant Medications ⁵	X	X	X	X	X	X
Adverse Events	X	X	X	X	X	X

¹Temperature and Sensation will be examined using a pinprick and cold sensory technique

² SF12 mental component and physical component, WOMAC and Knee Society Score, UCLA activity score, range of motion (and degree of varus/valgus deformity will be collected

³ Pain at rest, pain with activity, opioid consumption, nausea, pain disturbing sleep, location of most severe pain and satisfaction with regional anesthesia technique will be assessed

⁴ Pain with physical therapy, quadriceps strength, passive flexion/extension range of motion, postoperative quadriceps strength, postoperative adductor strength, and 10 meter walk test (gait velocity) using Kiio sensor

⁵ Medications that are taken at home regularly and prior to arrival on the day of surgery, surgery premedication, and all medications for nausea and pain will be recorded.

[List of abbreviations and definitions](#)

AE	Adverse event
CFNB	Continuous Femoral Nerve Blockade
CACNB	Continuous Adductor Canal Nerve Blockade
DSMC	Data Safety Monitoring Committee
PACU	Post-Anesthesia Care Unit
POD	Post-Operative Day
SAE	Serious Adverse Event
SSFNB	Single Shot Femoral Nerve Block
SSACNB	Single Shot Adductor Canal Nerve Block
TKA	Total Knee Arthroplasty

1. Introduction

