The patient will be visited in the PACU to assess pain, opioid consumption, nausea, duration of PACU stay, satisfaction with regional anesthesia technique and location of most severe pain. This information will be ascertained by questioning the patient and reviewing the subject's medical record. Many of these assessments are routinely done as standard of care at the current time.

Postoperative analgesia will generally consist of scheduled toradol, scheduled Tylenol, MS Contin or Oxycontin, oxycodone PRN, and celebrex 100-200 mg BID or any combination of these. Therapy may be altered for patients with history of drug intolerances or allergies or any other contraindication to a specific therapeutic agent. Extended release opioid therapy may also be excluded in select elderly patients at the discretion of the orthopedic team. This therapy represents standard of care and is not altered by study involvement.

24 and 48-hours post-operative Follow-up:

The patient will be assessed on the floor for pain at rest, pain with activity, opioid consumption, nausea, pain disturbing sleep, location of most severe pain and satisfaction with regional anesthesia technique will be ascertained at 24 and 48 hours following the surgical procedure by questioning patient and review of medical record. Pain will be assessed using a Numerical Rating Scale (NRS) (0-10) where 0 represents no pain and 10 represents the worst pain imaginable. Duration of hospitalization will be obtained from review of medical record. Subjects with new or persistent complaints at 48 hours post-surgery that could be related to the study procedures will be offered continued follow-up by telephone or in-hospital room visit until the complaints resolve. Follow-up procedures would depend greatly on the clinical presentation but could include imaging, specialist consultation or surgical intervention. Subjects without complaints will be given appropriate information for contacting the research team if such complaints arise.

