10.1 Adverse event definitions

Adverse event (AE)

An adverse event is defined as any untoward or unfavorable medical occurrence in a human subject including any abnormal sign, symptom, or disease temporally associated with the SSACNB or study procedure that appears or worsens during the study or study follow-up period. AEs may be anticipated (e.g., redness/soreness at injection site) or unanticipated (e.g., bleeding/infection/nerve damage). Adverse event information will be collected throughout the study from informed consent through resolution of the AE and documented on the case report form or the standard follow-up questionnaire.

All AEs (anticipated and unanticipated) will be recorded on one of the study data sheets (case report form or standard questionnaire) by a study investigator or study staff. In the event of an unanticipated AE, the primary anesthesia team caring for the subject will intervene as deemed appropriate. These are the same provisions that would be made for any non-study case and represents standard practice.

Serious adverse event (SAE)

A serious adverse event is defined as any adverse event that meets one of the following criteria:

- Results in death; OR
- Is life-threatening; OR
- Requires hospitalization or prolongs existing hospitalization; OR
- Results in significant or persistent disability or incapacity; OR
- Results in a congenital anomaly/birth defect

Given the minimal risk associated with the use of SSACB and the study procedures, no serious adverse events (SAEs) are anticipated. If a SAE occurs, the study primary and co-primary investigators will be immediately notified and further enrollment in the study will be halted until a full explanation of the cause of the event and its relationship to the SSACB and/or study procedure is understood. The IRB will be notified and re-initiation of study enrollment will not occur until approved by the IRB.

Unanticipated problem (UP)

An unanticipated problem is defined as an event that meets all of the following criteria:

- 1) Unexpected in severity, nature, or frequency given the research procedures and the characteristics of the subject population (i.e., problems that are not described in this protocol or other study documents); AND
- 2) Related or possible related to participation in the research; AND
- 3) Suggests that research places subjects or others at a greater risk of harm related to the research than was previously known or recognized.

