12.3 Study monitoring

After 30 subjects have been recruited, the study data will be reviewed by an independent anesthesiologist, blinded to study arm assignment, to ensure that no safety concerns exist. In the unlikely event that there is a safety concern, study recruitment will be halted and an independent data safety board, consisting of a minimum of three qualified practitioners, will be convened to evaluate the safety concern and make recommendations regarding changes to the study methods or termination of the study.

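### The independent safety review is set after 15 subjects in section 11.1 and after 30 in section 12.3, and serious adverse events are to be recorded to day 28 with no contact scheduled after the 48-hour visit

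*Combined protocol and SAP*

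**What the plan says.** **Safety review.** The section on the Data Safety Monitoring Committee (11.1) sets this rule: "After 15 subjects have been recruited, the study data will be reviewed by an independent anesthesiologist, blinded to study arm assignment". The section on study monitoring (12.3) sets this one: "After 30 subjects have been recruited, the study data will be reviewed by an independent anesthesiologist, blinded to study arm assignment". Both sections go on to say that a safety concern stops recruitment and brings together a panel of at least three practitioners.

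**SAE window.** The section on recording and reporting adverse events (numbered 10.1 in the text, 10.4 in the table of contents) says that all SAEs from consent "through and including 28 calendar days after the procedure will be recorded".

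**Scheduled contact.** The adverse-event row of the schedule of activities ends at Visit 6, "48 hours post-op +/- 6 hours". For the time after that visit, section 7 (24- and 48-hour follow-up) says: "Subjects with new or persistent complaints at 48 hours post-surgery that could be related to the study procedures will be offered continued follow-up". For everyone else: "Subjects without complaints will be given appropriate information for contacting the research team if such complaints arise".

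**Consequence of an SAE.** Section 10.1 (Adverse event definitions) says what follows an SAE: "further enrollment in the study will be halted until a full explanation of the cause of the event". Any link with the block or with study procedures must be clear as well, and restarting needs IRB approval.

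**Start of adverse-event collection.** Section 10.1 (definitions): "Adverse event information will be collected throughout the study from informed consent through resolution of the AE". The recording section instead starts non-serious events when study procedures begin.

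**The concern.** The two review paragraphs are close to word-for-word copies with different trigger counts. Neither speaks of a first and a second look or points to the other. A site working from 12.3 alone would hold its first independent review 15 subjects later than one working from 11.1.

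The SAE point is a gap in ascertainment, not a contradiction. The plan promises a complete record of SAEs for four weeks but schedules observation for about two days. After that it depends on a complaint already present at 48 hours, or on the subject making contact. A subject who is well at 48 hours and hospitalized on, say, day 10 becomes known only by calling in.

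This matters because the trial's strongest safeguard, the enrolment halt, is triggered by SAEs. Hospitalization is one of the SAE criteria, and section 10.3 classes any fall as probably related to study procedures. Both can happen after discharge. A fall is an SAE only if it meets one of the listed criteria, but a fall leading to readmission would.

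The differing start points for adverse-event collection are a minor inconsistency with little practical effect.

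**Working it through.** The plan derives no figure on this point. The counts and times below are stated in it, and the rest is arithmetic on them.

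**1. The two review paragraphs side by side**

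| Feature | Section 11.1 | Section 12.3 |
|---|---|---|
| Trigger | 15 recruited | 30 recruited |
| Reviewer | Independent anesthesiologist, blinded to arm | Same |
| Purpose | Check for safety concerns | Same |
| If there is a concern | Recruitment halted, panel of at least three | Same |
| Name of panel | Data Safety Monitoring Committee | Data safety board |
| Mention of another review | None | None |

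Only the trigger and the panel's name differ.

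**2. Size of the difference in trigger**

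Inputs: 60 subjects (section 3) and 1:1:1 allocation (section 5).

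- Share of enrolment: 15/60 = 25%; 30/60 = 50%.
- Expected per arm: 15/3 = 5; 30/3 = 10.
- Extra subjects before the first look if only 12.3 is followed: 30 − 15 = 15.

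The chance that the reviewed subjects include at least one event is 1 − (1 − p)^n, where p is the per-subject event risk. The documents give no event rate, so p is an assumed range.

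| Assumed p | n = 15 | n = 30 |
|---|---|---|
| 2% | 1 − 0.98^15 = 26.1% | 1 − 0.98^30 = 45.5% |
| 5% | 1 − 0.95^15 = 53.7% | 1 − 0.95^30 = 78.5% |
| 10% | 1 − 0.90^15 = 79.4% | 1 − 0.90^30 = 95.8% |

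**3. SAE window without scheduled contact**

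Inputs: recording to day 28 (recording section); last visit at 48 h ± 6 h (schedule of activities).

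- Last visit: 48 − 6 = 42 h = 1.75 days, to 48 + 6 = 54 h = 2.25 days.
- Unobserved time: 28 − 2.25 = 25.75 days, to 28 − 1.75 = 26.25 days.
- As a share: 25.75/28 = 92.0%; 26.25/28 = 93.8%.

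**4. Does other text close the gap?**

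- Section 7 has length of stay and medication use extracted from the medical record. That can run past 48 hours, but it covers the hospital stay and not events after discharge.
- Section 10.1 (definitions) follows an adverse event to resolution, which presupposes that the event is already known.
- The same section mentions a standard follow-up questionnaire but gives it no time point.

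None of these provides for contact with, or a record check on, every subject between 48 hours and day 28.

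**The case against.** **The two review sections can both be obeyed.** One can review after 15 and again after 30. This stands: the text is ambiguous, not impossible to follow, and near-identical wording suggests an editing slip without proving one. The sections still need to say which is meant, because neither tells its reader that the other exists.

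**The review is not the only safeguard.** A known SAE halts enrolment whatever the count, and the protocol anticipates none. This limits the harm from the first point: what the review adds is mainly non-serious or cumulative concerns. The probabilities above do not separate serious from non-serious events. They show that the two triggers are not interchangeable; they do not measure harm.

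**Recording SAEs to day 28 is not a promise to seek them out.** A passive route exists, since subjects are told how to make contact. That is fair, and it is why the point is called a gap. But the recording rule covers all SAEs, and a route that relies on subjects volunteering information cannot deliver that. An absence of reports could not be told apart from an absence of events.

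**The case report form (Appendix B) was not available for this review, and the timing of the follow-up questionnaire is not stated.** Either might contain a later check. Nothing in the available text shows one, and the schedule of activities, where it would belong, has none.

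**Conclusion.** Both points hold. The plan gives two triggers, at 25% and 50% of enrolment, for what reads as a single review, and does not say whether one or two are intended. It also requires complete SAE recording over 28 days while scheduling no contact for 92% to 94% of that time, so late SAEs may be missed and the trial's own enrolment halt left untriggered.

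The trigger fractions and the contact gap follow directly from the documents. Only the chances of seeing an event rest on assumed risks of 2% to 10%, and the conclusion does not depend on them. The effect is on safety oversight. These points should be corrected, but they do not threaten the trial's efficacy result.

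**What to change.** 1. Reconcile sections 11.1 and 12.3. Either give the same single trigger in both, or state in both that there are two reviews and when each takes place. Use one name for the panel. Which schedule is intended is for the sponsor to decide.
2. Add a day-28 row to the schedule of activities: one telephone call or medical-record check per subject for SAEs, with matching text in section 7 and in the recording section. A check of the site's own records alone may miss events treated elsewhere, which a call would be more likely to find.
3. Align the start of adverse-event collection in section 10.1 (definitions) and the recording section, stating whether non-serious events count from consent or from the first study procedure.

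Cost: short wording changes in the sections named, one added schedule row, and the written IRB approval that section 12.6 requires for protocol changes. The added work is up to 60 calls or record checks. At an assumed 5 to 15 minutes each, 60 × 5 = 300 minutes (5 hours) to 60 × 15 = 900 minutes (15 hours) over the whole trial. Sample size, randomization and the POD 1 walk test are unchanged.

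Stating that SAEs after 48 hours are found only by subject report would cost less. It would make the plan honest about the gap but would not close it, and the enrolment halt would still depend on subjects calling in.

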12.1 Good clinical practice

The study will be conducted in accordance with FDA and ICH guidelines for Good Clinical Practice. All study staff will be thoroughly familiar with the contents of this protocol and associated trial materials.

12.2 Data quality assurance

Paper records containing personal identifying information will be stored in the study primary investigator's locked office and destroyed after seven years as required by UWHC.

12.3 Study monitoring

After 30 subjects have been recruited, the study data will be reviewed by an independent anesthesiologist, blinded to study arm assignment, to ensure that no safety concerns exist. In the unlikely event that there is a safety concern, study recruitment will be halted and an independent data safety board, consisting of a minimum of three qualified practitioners, will be convened to evaluate the safety concern and make recommendations regarding changes to the study methods or termination of the study.

12.4 Ethical consideration

The study will be conducted in accordance with ethical principles founded in the Declaration of Helsinki. The IRB will review all appropriate study documentation in order to safeguard the rights, safety and well-being of the subjects. The study will only be conducted at sites where IRB approval has been obtained. The protocol, informed consent form, written information given to the patients, safety updates, annual progress reports and any revisions to these documents will be provided to the IRB by the investigator.

12.5 Patient confidentiality

Subject privacy and confidentiality will be ensured by restricting access to personal identifying study data only to members of the research team. In addition, as mentioned previously, recruitment will take place in the subject's cubicle or room in the preoperative or preprocedural holding area with the curtain drawn or door closed, in a tone of voice insufficient for others to overhear the conversation and in the presence of only those immediately accompanying the subject and those who are directly involved with the subject's care.

12.6 Investigator compliance

The investigator will conduct the trial in compliance with the protocol approved by the IRB. Changes to the protocol will require written IRB approval prior to implementation, except when the modification is needed to eliminate an immediate hazard(s) to subjects.

Appendix D – Kiiو Information Sheet

Kiiو Inc. began the Phase I “WiFi-enabled hand-portable real-time force sensor to objectively assess strength” project on March 1, 2013, and concluded the project August 1, 2013. (Expenditures prior to March 1, 2013 were borne by Kiiو.) This is the final summary report for the Phase I project. **Kiiو successfully completed all Phase I Aims.** No changes were made to the project’s goals and aims as outlined in the original Phase I Research Strategy.

The **overall project goal of Phase I** was to refine, miniaturize, and test a clinically relevant prototype device (the kiiو™) that would be able to accurately and consistently measure force over time so as to provide kinetic measurement of muscle strength, continuously tracking variability in strength over the entire range of movement to enable a complex analysis of muscle performance. Our goals for the kiiو were that it should (1) provide wireless data output via proprietary software to PCs in real-time, allowing a clinician to track and interpret data as the patient generates it; (2) offer high inter-rater reliability for consistency between clinicians; (3) interface with commonly used rehabilitative equipment such as resistance cables; (4) be hand-portable, not requiring dedicated clinic space; (5) be cost effective in terms of initial investment and clinician training; and (6) be rugged enough to withstand the rigors of daily use while maintaining accuracy. Its clinical significance would be to provide a fast, objectively valid, reliable, portable and cost-effective method of strength assessment, thus eliminating a significant barrier to the implementation of evidence-based evaluation and outcome measurement in prescriptive rehabilitative exercise.

Aim 1: Develop and prototype a functional, integrated kiiو to measure continuous muscle force output and translate this information to a real-time digital data stream. Kiiو began with a high-level,

Figure 1

logical engineering model of the device in block diagrams depicting a device able to generate force readings using off-the-shelf components and proprietary software. We developed an electrical and logical design for a printed circuit board (PCB) using Computer assisted engineering software (CAE). We created protocols to test the PCB design and identify and remove errors, while keeping functional design elements. Successive iterations eliminated design errors and added functionality, leading to a stable design. We wrote firmware (hard-coded proprietary programming) to control the microprocessor, and synchronized the WiFi transceiver and a wireless router to ensure the proper communication between the kiiو and a PC, necessary to display data in real-time.

Figure 2

Table 2: Phase I, Aim 1 outcomes

Task	Objective outcomes/Milestones	Result
1.1	Hand-portability: kiio prototype will be no larger than 7 x 4 x 10 cm and no heavier than 150 g.	Success. kiio weighs just 120g and measures 7cm wide x 9cm high x 4cm deep (see Figure 1)
1.2	Design elements: kiio prototype will include: a) a strain gauge, b) a microprocessor, c) a wireless WiFi transmitter, and d) an Li-ion battery	Success. kiio includes a strain gauge, microprocessor, wireless WiFi transmitter and a rechargeable Li-ion battery
1.3	Integration with commonly-used rehabilitative exercise equipment: kiio prototype will connect to a variety of commonly used resistance mechanisms	Success. kiio connects directly to commonly-used resistance mechanisms such as elastic cables, straps, and portable handles (see Figure 2)
1.4	WiFi data delivery: kiio prototype will send a continuous, real-time digital WiFi data stream to a PC	Success. kiio sends a continuous, real-time digital data stream wirelessly over WiFi of force readings over time to a computer as described and tested in Aims 2 & 3

Table 3 - Device Results

Load Cell	Kiio #7E	Delta
0.1	0.3	0.2
5.1	5.2	0.1
10.3	10.3	0.0
15.2	15.0	-0.2
20.7	20.4	-0.3
25.8	25.7	-0.1
30.8	30.9	0.1
35.8	36.4	0.6
40.9	41.4	0.5
46.0	46.3	0.3
51.3	51.6	0.3
56.0	56.6	0.6
61.0	61.5	0.5
66.2	66.4	0.2
71.3	71.4	0.1
76.4	76.6	0.2
81.3	81.6	0.3
86.5	86.6	0.1
92.1	92.1	0.0
97.4	97.1	-0.3
103.1	102.8	-0.3

Aim 2: The kiio prototype will be iteratively calibrated to ensure that it properly reads known force and can be set to ignore a tare weight. The kiio requires calibration for precision and consistency; without it, accuracy and test-retest reliability would be jeopardized. Kiio used a six step process (**Figure 3**) to facilitate this Aim. Ensuing successful completion of the setup steps, we tested 10 devices by repeatedly hanging the 20 plates (one at a time) on each device. With each additional plate the weight was allowed to settle and kiio reported a static force reading to the PC where it was recorded. Cumulative readings of these weights were also taken using a commercially available load cell for comparison.

Summary of Test Results: All ten devices were initially calibrated and had tare weights set. Nine out of ten devices were accurate to within 2% (1.0 lb) on the first pass (i.e., without the need for a re-calibration or re-tare). Their average deviation from the load cell ranged from 0.11 lbs. to 0.83 lbs. with no readings deviating from expected results by more than 1.0 lb. Only one device (#7E) exceeded our target tolerance, with an average under-weight of 1.18 lbs. per reading. The readings from device #7E were consistently low. Consequently, the device was re-calibrated, re-tared, and the tests were rerun and kiio #7E yielded an average deviation of 0.14 lbs. from the expected results (see **Table 3**). The initial readings of device #7E suggests that our technician did not properly do a full tare (step #6 above) prior to conducting tests.

Figure 3 - Steps to prepare kiio for static testing

Step	Action
1	Establish two sets of known weights a Kettlebells for creating calibration curves b ~5 lb. plates for static device testing
2	Create calibration software for kiio
3	Establish calibration equation for each device
4	Calibrate kiio by loading equation into device memory
5	Create Tare (Zero-out) software for kiio
6	Tare kiio by loading offset into device memory

Table 4 – Phase I, Aim 2 outcomes

Tas k	Objective outcomes/Milestones	Result
2. 1	kiio will correctly measure force and transmit accurate data within the larger of either 2% absolute error or 1 lb.	Success. Kiio extended the number of test kiio devices from 4 to 10. All devices successfully completed calibration on their first attempt, and 100% of the force readings were within acceptable tolerance.
2. 2	Redefine of zero point: kiio prototype will be able to accept a constant offset and thereby redefine the zero point, or a given tare weight.	Success. A connector was hung from the device and an offset was sent from the PC to the kiio to tare the weight back to 0.0 lbs. 100% of devices were successful. This process was repeated with various connectors, ranging in weight from 0.2 lbs. to 5.1 lbs. Again, 100% of devices were successful in the tare process.
2. 3	Maximum static weight: kiio device will be able to accurately register static weights from 0.0 to 100.0 lbs.	Success. The commercial load cell registered a total of 103.1 lbs (99.7% accurate, with possible variability derived from cumulative rounding error over 20 plates). 9 of the 10 kiio devices were accurate to within tolerance on the 1 st attempt (i.e., without a need for re-calibration). 100% of kiios met specification after recalibrating and re-taring one device (#7E).

Aim 3: Verify the prototype measurements are valid and reliable over high use and extended sessions. The kiio device must be used rigorously over a high number of repetitions to ensure it maintains accuracy and reliability in order to provide valid and consistent measurements through expected durations of use. The aim contained two stages: (1) Compare the kiio to a calibrated strain gauge for consecutive cycles to analyze statistical variances; and (2) examine accuracy after 20 days of use.

[figure not shown]

Figure 4

Kiio created a motorized test fixture (Figure 4) to exercise 6 devices with a series of cyclical tests. Testing software was used to collect force readings from kiio devices and a commercial load cell. Data was plotted in real-time to the screen, as well as logged to a Microsoft Access

for
Test
run
device through a series of ~500
applying a force up to a threshold
relaxing that force back to a lower limit. Peak values from the kiio for each cycle was analyzed against
the peak values from the load cell. 100% of the kiios were within this Aim's accuracy threshold for 100%
of these cycles.

Additional analysis of the full 33,000+ samples per device (beyond the scope of the original Aim), demonstrated that the device not only reports peak forces accurately during dynamic use, but tracks well throughout the entire force curve. Figure 5 is a close-up of data from a kiio device (shown in green) plotted against the load cell (in red). The graph shows that as forces range from 8-36 lbs., the kiio tracks the commercial load cell with amazing accuracy. Figure 6 shows, for each device, the # of cycles tested and the linear regression analysis R^2 and ICC statistics. A typical scatter plot and residual plot is also

[figure not shown]

Figure 5

database
further
analysis in
Microsoft
Excel.
#1 was to
each
cycles of
and then

database
further
analysis in
Microsoft
Excel.
#1 was to
each
cycles of
and then

database
further
analysis in
Microsoft
Excel.
#1 was to
each
cycles of
and then

Additional analysis of the full 33,000+ samples per device (beyond the scope of the original Aim), demonstrated that the device not only reports peak forces accurately during dynamic use, but tracks well throughout the entire force curve. Figure 5 is a close-up of data from a kiio device (shown in green) plotted against the load cell (in red). The graph shows that as forces range from 8-36 lbs., the kiio tracks the commercial load cell with amazing accuracy. Figure 6 shows, for each device, the # of cycles tested and the linear regression analysis R^2 and ICC statistics. A typical scatter plot and residual plot is also

Device ID	Cycles	R^2	ICC(3,1)	95% CI
60	504	0.98	0.989	0.987-0.990
67	500	0.99	0.995	0.995-0.996
69	500	0.99	0.994	0.993-0.995
6D	500	0.99	0.995	0.994-0.996
75	493	0.99	0.993	0.992-0.994
7E	501	0.99	0.996	0.996-0.997

shown.

Kiio also conducted multiple tests to determine if readings drift over time. In addition to the specified 20 days of dynamic load testing for durations ranging from 10 minutes to 1 hour, we also performed static weights tests 3 months after the device's original calibration. Our conclusion: there's no discernible drift after 3 months of use. Figure 7 is a summary of statistics for the 20-day testing on 4 kiio devices:

[figure not shown]

Figure 6

Figure

Device ID	Day 1			Day 20		
	R ²	ICC(3,1)	95% CI	R ²	ICC(3,1)	95% CI
60	0.97	0.982	0.973-0.988	0.98	0.99	0.985-0.993
67	0.97	0.985	0.977-0.990	0.98	0.988	0.982-0.992
69	0.98	0.992	0.988-0.995	0.99	0.995	0.993-0.997
7E	0.99	0.995	0.993-0.997	0.99	0.989	0.983-0.992

[figure not shown]

Table 5 – Phase I, Aim 3 outcomes

Tas k	Objective outcomes/Milestones	Result
3. 1	Measurement validity: kiiot prototype will accurately measure forces over time as compared to industry calibrated strain gauge (with no more than 2% absolute error, and $R^2 \geq 0.98$) over the course of 500 cycles.	Success. 6 out of 6 devices passed this test with 100% of samples taken within this specified tolerance (2998 peak readings from the kiiot devices were within 1.0 lb. of the load cell value). The R^2 and ICC numbers also verify the accuracy of the kiiot device.
3. 2	Reliability: kiiot prototype will demonstrate high intra-class correlation coefficients ($ICC \geq 0.99$) comparing baseline to tests that recur over time, throughout extended testing periods (10 min. - 1 hr. continuous use)	Success. The results of dynamic testing produced the same consistency that static testing exhibited: All readings were within the tolerance of this Aim; kiiot is ready to be ruggedized and enter the next phase of testing.

Kiiot has shown prototype kiiot devices provide accurate measurements for thousands of use cycles over the course of weeks of continuous use, and that the kiiot is capable of use with similar frequency to manual muscle testing in a typical physical therapy clinic by one therapist over the course of a month with no loss of accuracy.

Successful Completion: By successfully completing all of the Aims set forth in Phase I, Kiiot has demonstrated the feasibility of a hand-portable wireless kiiot device prototype. Kiiot provides objectively valid, reliable measurements of force over time, and accurately transmits this data wirelessly to a PC. This is a major step in Kiiot's overall vision of developing the integrated kiiot FLEX System: combining the kiiot device and kiiot FLEX software for Physical and Occupational Therapists (PT/OT's). In Phase II Kiiot proposes to further refine and ruggedize the kiiot for clinical use, to develop kiiot FLEX, create an integrated animated exercise library, and to test the system in clinical settings. Concurrently, we will be completing 510k premarket notification on the kiiot FLEX System. The fully developed kiiot FLEX System will be positioned to provide PT/OT's a fast, objectively valid, reliable, portable and cost-effective method of strength assessment. This will enable PT/OT's to integrate evidence-based assessments into their practices which could significantly reduce the disability burden on the U.S. population (both individual and societal costs) by enhancing clinical efficiency and increasing positive patient outcomes.
